2.4.2 Outliers

Every outlier will be checked at data validation before unblinding the study. Interval variables will be checked by visual inspection using histograms, box-plots or scatter plots, and verified by referral back to source documents. If the values are not erroneous, they will be included in the analysis.

2.4.3 Site Effects

This is a single centre study, therefore there will be no controlling for site effects.

2.4.4 Assessment of Model Fit

Q-Q plots and histograms will be generated for the evaluation of normality of the residuals of mixed models. If the residuals are highly skewed, ranks, log or other transformation of the dependent variable will be performed.

2.4.5 Adjustments of Multiple Comparisons

Since there are only two study groups involved, there will be no pairwise comparisons requiring adjustment. There will be no adjustment for multiple outcomes.

3. Reference List

2. Mark Mather, Linda A. Jacobsen, Kelvin M. Pollard. Aging Baby Boomers to Face Caregiving, Obesity, Inequality Challenges [Internet]. population reference bureau; 2016 Jan. Available from: <https://www.prb.org/unitedstates-population-bulletin/>
3. Diabetes [Internet]. world health organization; 2018 Oct. Available from: <https://www.who.int/news-room/fact-sheets/detail/diabetes>
4. RiaGev® [Internet]. bioenergy life science Inc.; Available from: <http://bioenergylifescience.com/#products>
5. Compound Summary for CID 10975657 D-Ribose [Internet]. National Center for Biotechnology Information; [cited 2019 Feb 28]. Available from: <https://pubchem.ncbi.nlm.nih.gov/compound/D-ribopyranose#section=Food-Additives-and-Ingredients>
7. Niacin Fact Sheet for Health Professionals [Internet]. National Institutes of Health; 2019. Available from: <https://ods.od.nih.gov/factsheets/Niacin-HealthProfessional/#h9>

4. Appendix

Table 3. Summary of outcomes and analysis methods

Outcome	Data type	Between groups analysis methods
Primary Outcome		
1. The change in whole blood NAD+ levels from baseline to day 8 when supplemented with RiaGev™ or comparator.	Interval	Repeated-measures mixed ANCOVA
Secondary Outcomes		
1. The change in serum glucose and insulin as assessed by an Oral Glucose Tolerance Test (OGTT) at t=0, 15m, 30, 45m, 60m, 90m and 2h after a 7-day supplementation with either RiaGev™ or comparator	Interval	Repeated-measures mixed ANOVA (change in concentrations); mixed ANOVA (iAUC)
2. The change in serum Glutathione/Glutathione disulfide (GSH/GSSG) ratio after a 7-day supplementation with either RiaGev™ or comparator	Interval	Repeated-measures mixed ANCOVA
3. The change in serum adenosine triphosphate/ adenosine monophosphate (ATP/AMP) ratio after a 7-day supplementation with either RiaGev™ or comparator	Interval	Repeated-measures mixed ANCOVA
4. The change in salivary cortisol after a 7-day supplementation with either RiaGev™ or comparator	Interval	Repeated-measures mixed ANCOVA
5. The change in Checklist Individual Strength (CIS) Questionnaire outcome after a 7-day supplementation with either RiaGev™ or comparator	Interval	Repeated-measures mixed ANCOVA
Safety Outcomes		
1. Proportion of participants experiencing at least one adverse event when taking RiaGev™ or comparator	Nominal	Chi Square or Fisher's Exact Test
2. The effect of supplementation with RiaGev™ or comparator on vital signs (blood pressure and heart rate) and anthropometrics (weight and BMI) from pre-supplementation to Day 7 post-supplementation a. blood pressure (BP) b. heart rate (HR)	Interval Interval	Not applicable
3. The effect of supplementation with RiaGev™ or comparator on clinical chemistry from screening to end-of-study as assessed by a. alanine aminotransferase (ALT) b. aspartate aminotransferase (AST) c. total bilirubin d. creatinine e. sodium (Na)	Interval Interval Interval Interval	Not applicable

Outcome	Data type	Between groups analysis methods

 f. potassium (K) g. chloride (Cl) h. fasting glucose i. estimated glomerular filtration rate (eGFR) 	
 Interval Interval Interval Interval Interval 	

4. The effect of supplementation with RiaGev™ or comparator on hematology from screening to end-of-study as assessed by
 
 a. white blood cell (WBC) count b. neutrophils c. lymphocytes d. monocytes e. eosinophils f. basophils g. red blood cell (RBC) count h. hemoglobin i. hematocrit j. platelet count k. mean corpuscular volume (MCV) l. mean corpuscular hemoglobin (MCH) m. mean corpuscular hemoglobin concentration (MCHC) n. red cell distribution width (RDW) 	
 Interval Interval Interval Interval Interval Interval Interval Interval Interval Interval Interval Interval Interval Interval Interval 	Not applicable
Demographic Characteristics & Other Outcomes		
1. Age	Interval	Not applicable
2. Gender	Nominal	Not applicable
3. Ethnicity	Nominal	Not applicable
4. Overall Compliance	Interval	ANOVA
5. Food Records (calories, fat, sodium, carbohydrates, saturated fat, cholesterol, protein, fiber, sugars, potassium, Vitamins A, B6, B12, C, D and E, thiamin, riboflavin, niacin, folic acid, calcium, iron, magnesium, zinc, alcohol, folate and transfat	Interval	Repeated-measures mixed ANCOVA

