6 STUDY DESIGN

This will be a randomized, double-blind, comparator-controlled, crossover, safety and efficacy study conducted at Prism Clinical Research Clinic, Saint Paul, MN, USA, a KGK Science Inc. partner.

The planned sample size for this study is 18, crossing over once is equivalent to 36 participants. To evaluate the outcomes, study assessments will be conducted as per the schedule of assessments in section 1.3

Study Arm	Number of Participants
RiaGev [™] → Comparator	N = 9
Comparator→ RiaGev [™]	N = 9
Total	N = 18

investigate the safety and efficacy of RiaGev[™] in healthy adults

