9.7 Washout period (Day 9 to Day 15+3 Days)

Participants will undergo a 7-day washout prior to visit 6.

Participants are reminded to follow the dietary guidelines 15.3, avoid the consumption of the medications and supplements as per 7.3.1 and 7.3.2, collect saliva the morning of the next in-clinic visit, and maintain current level of physical activity and maintain and record sleep schedule.

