9.11 Visit 9 – End of the Study (period 2- Day 8+1 Day)

Participants will return to the clinic fasted (8h) for Visit 9 assessments with unused investigational product, completed Subject sleep and treatment diary, saliva kit, and food records.

Visit 9 assessments include:

- 1. Review concomitant therapies
- 2. Seated resting blood pressure and heart rate measurements
- 3. Weight measurements (BMI calculation)
- 4. Return unused investigational product in the original packaging and remnants and calculate compliance by counting the returned unused investigational product
- 5. Physical Exam
- 6. Collect Food Record and Subject sleep and treatment diary for review
- 7. Return saliva collection kit
- 8. Review AEs
- 9. Collect blood sample at T=0 (pre-meal) for fasting serum glucose, insulin, Complete Blood Count (CBC), electrolytes (Na, K, Cl), eGFR, creatinine, AST, ALT, total bilirubin
- 10. Administer the investigational product
- 11. Standardized meal provided (see appendix 15.2)
- 12. Collect post-meal blood sample for serum glucose and insulin analysis at:
 - a. T=15min
 - b. T= 30min
 - c. T=45min
 - d. T=60min
 - e. T=90min
 - f. T=2hrs
- 13. Collect blood sample at T=2 hours (post-meal) for NAD+
- 14. (Optional) Measure NADH with skin fluorescence
- 15. Complete treadmill exercise protocol (Section 9.12.7)
- 16. (Optional) Measure NADH with skin fluorescence
- 17. Collect blood sample for GSH/GSSG and ATP/AMP Analyses
- 18. Administer CIS questionnaire

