11.3.2 Safety

For adverse events, a descriptive analysis will be given. Adverse events will be presented in a frequency table by category and treatment. Furthermore, description, frequency, severity and causality will be reported for each adverse event.

Continuous safety parameters (e.g. hematology, clinical chemistry, heart rate and blood pressure) will be summarized using a table including mean, standard deviation, median, minimum value, and maximum value for each measurement point. The changes from baseline will also be summarized similarly.

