2.3.2 Other Safety Variables

Clinically significant measurements for the variables listed below will be discussed as part of the final study report.

1. Vital signs (blood pressure (BP) and heart rate (HR))
2. clinical chemistry (alanine aminotransferase (ALT), aspartate aminotransferase (AST), total bilirubin, creatinine, electrolytes (Na, K, Cl), fasting glucose and estimated glomerular filtration rate (eGFR))
3. hematology (white blood cell (WBC) count with differential (neutrophils, lymphocytes, monocytes, eosinophils, basophils), red blood cell (RBC) count, hemoglobin, hematocrit, platelet count, RBC indices (mean corpuscular volume (MCV), mean corpuscular hemoglobin (MCH), mean corpuscular hemoglobin concentration (MCHC), red cell distribution width (RDW))

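### SAP Table 3 defines the product effect on safety laboratory values from screening to Visit 9, an interval that for every completer covers both products and the washout

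*SAP*

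**What the plan says.** SAP Table 3 words Safety Outcome 3 as the effect of supplementation with either product "on clinical chemistry from screening to end-of-study as assessed by" ALT, AST and seven further analytes. Safety Outcome 4 is the corresponding effect "on hematology from screening to end-of-study as assessed by" the blood count components. Both rows give the between-group method as not applicable. The vital-signs row just above them uses a different interval, "from pre-supplementation to Day 7 post-supplementation".

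Other sections bear on the same variables:

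- SAP 2.1 summarises all data by study group and visit. It defines change in an interval endpoint as the visit value minus the pre-supplementation value.
- SAP 2.3.2, the section for these variables, says only: "Clinically significant measurements for the variables listed below will be discussed as part of the final study report".
- Protocol 11.3.2 promises mean, SD, median, minimum and maximum at each measurement point, and adds: "The changes from baseline will also be summarized similarly".
- Protocol 6 sets out a two-sequence crossover with 9 participants per sequence: "The planned sample size for this study is 18, crossing over once is equivalent to 36 participants". Between the periods, "Participants will undergo a 7-day washout prior to visit 6".
- The schedules in protocol 1.3 and SAP Table 2 place the safety panel at Visits 1, 5, 6 and 9. It is not drawn at Visit 2, the Period 1 baseline.

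**The concern.** In a crossover, a product effect is read from a change within the period in which that product was taken. Screening comes before both products and Visit 9 comes after both. A change between those two visits mixes the Period 2 product, any residue of the Period 1 product, and drift over five weeks or more.

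Safety is half of the stated study objective, and these panels are its main quantitative evidence. An analyst who follows Table 3 and SAP 2.3.2 literally could report screening-to-Visit 9 changes, discuss the clinically significant values, and never produce a laboratory change by product.

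**Working it through.** The plan states no figure for this outcome, so there is none to reproduce. The check takes the timeline first, then what each interval can estimate.

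**1. Timeline and exposure (protocol 8.5, 9.1, 9.7, 9.11).**

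- Screening falls on Day -45 to Day -14 and Period 1 dosing starts on Day 1. The washout is Day 9 to Day 15, so Visit 6 is nominally Day 16 and Visit 9 is Day 16 + 7 = Day 23.
- Screening to Visit 9 is 23 + 14 = 37 days at the shortest and 23 + 45 = 68 days at the longest, before visit and washout windows. (Protocol 9.14 gives about 20 days for the same span, which does not fit this calendar.)
- Each period has one dose on Day 1, two a day on Days 2 to 7, and one on Day 8: 1 + 12 + 1 = 14. The Day 8 dose follows the fasting draw. A fully compliant completer therefore reaches the Visit 9 panel after 14 doses of the first product and 13 of the second.

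**2. Visit 9 minus screening.** Let a and b be the shifts at end of dosing on RiaGev and comparator, p the drift from screening to Visit 9, and rA and rB the residue at Visit 9 of a product taken in Period 1.

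- RiaGev first: p + b + rA
- Comparator first: p + a + rB
- Pooled, 9 and 9: p + (a + b)/2 + (rA + rB)/2

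Set p = 0 with complete washout (rA = rB = 0). If RiaGev causes the shift (a = d, b = 0), the pooled mean is (9×0 + 9×d)/18 = d/2. If the comparator causes it (a = 0, b = d), the pooled mean is (9×d + 9×0)/18 = d/2. For an assumed d of 5 units, both give 2.5. If the effect persists fully to Visit 9, both give 5. The pooled figure cannot show which product was responsible.

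Split by sequence, comparator-first minus RiaGev-first is (a − b) − (rA − rB). With complete washout this is a − b, from 9 against 9. With full persistence it is 0. Neither a nor b can be separated from p.

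**3. Within-period changes.** Let p1 and p2 be the drifts over the two periods.

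- Visit 5 minus screening: p1 + a (RiaGev first), p1 + b (comparator first)
- Visit 9 minus Visit 6: p2 + b (RiaGev first), p2 + a (comparator first)
- Pooled by product: RiaGev a + (p1 + p2)/2, comparator b + (p1 + p2)/2, difference a − b

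With no drift, a 5-unit RiaGev effect gives 5 and 0, and a 5-unit comparator effect gives 0 and 5. If a Period 1 residue is still decaying between Visits 6 and 9, the Period 2 changes are disturbed, but the Period 1 changes alone still estimate a − b.

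**4. Precision.** Assume 18 completers, complete washout and a common correlation ρ between any two panels. In units of the analyte's SD, a change has SD √(2(1 − ρ)). The sequence split has SE SD×√(2/9). The within-participant contrast has SE √2×SD/√18.

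| ρ (assumed) | Sequence split | Within participant |
|---|---|---|
| 0.3 | 0.558 | 0.394 |
| 0.5 | 0.471 | 0.333 |
| 0.7 | 0.365 | 0.258 |

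The ratio is √2 throughout: even under its most favourable assumption, the split is about 41% less precise in SE.

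**5. Consistency.** The vital-signs row and SAP 2.1 both measure from pre-supplementation; the two laboratory rows measure from screening across both periods. SAP 2.1 does not assign pre-supplementation to a visit. Protocol 11.3 takes baseline as Day 1, where the safety panel is not drawn, so the Period 1 laboratory baseline is left undefined. Fasting glucose is the exception, since protocol 9.3 draws it at Visit 2.

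**The case against.** The strongest reply is that SAP 2.1 already covers this. It applies to all data, calls for summaries by study group and visit, and defines change from pre-supplementation. SAP 2.2.2 lists study group beside sequence and period in the iAUC model, so study group there means product. On that reading Visit 5 and Visit 9 values are summarised by product whatever Table 3 says. The words in Table 3 may simply mark the span over which panels are drawn, as protocol 9.14 does when it totals blood volume. No passage tells the analyst to pool over sequences, so d/2 is conditional on a step the plan does not state.

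Much of this stands. A reader might infer that no laboratory effect can be attributed to either product. The documents do not support that: panels exist at Visits 5 and 6, the general rules permit per-product summaries, and even the sequence split recovers the contrast if washout is complete. Nor has every participant taken both products by the end; protocol 7.4 allows withdrawal without replacement, so this holds for completers only.

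A reader might also infer that harm would go unseen. Protocol 10.1.4 requires the investigator to assess every abnormal value and to record clinically significant treatment-emergent ones as adverse events, and SAP 2.3.2 is not limited to Visit 9. What could be missed is a mean shift below clinical significance.

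The reply does not remove the conflict. SAP 2.1 contradicts the laboratory rows, and no rule says which prevails. Protocol 11.3.2 specifies presentation by treatment for adverse events but not for laboratory values. SAP 2.3.2 promises less than the protocol does.

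**Conclusion.** The interval in Table 3, Safety Outcomes 3 and 4, is the wrong one for a product effect in this design and should be changed. The fault lies in the outcome definition and the reporting commitment, not in the data. No laboratory hypothesis test is planned, so no p-value or primary conclusion changes.

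The size depends on how the analyst proceeds. Pooling halves a transient effect and leaves its source unknown; splitting by sequence keeps the contrast but costs a factor of √2 in standard error and rests on complete washout. The d/2 result assumes 9 completers per sequence, no drift and full washout. The precision figures further assume equal correlation between panels, a value the documents do not give. The inconsistency with the vital-signs row and SAP 2.1 needs no assumption.

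**What to change.** - **Table 3, Safety Outcomes 3 and 4:** replace the screening-to-end-of-study interval with within-period change by product received, namely screening to Visit 5 for Period 1 and Visit 6 to Visit 9 for Period 2.
- **SAP 2.3.2:** commit to the protocol 11.3.2 statistics (mean, SD, median, minimum, maximum) for values and changes, by product, alongside the discussion of clinically significant measurements.
- **Baseline:** state that screening is the Period 1 baseline for these panels because Visit 2 has none. Fasting glucose is drawn at Visit 2 and can use that value.

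The cost is SAP wording and one table, with no new samples. The small downside is a Period 1 baseline taken nominally 15 to 46 days before Day 1 (1 + 14 and 1 + 45), so Period 1 changes carry more drift than Period 2 changes. Showing the two periods separately beside the pooled figures would make that visible.
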